Cover: Protocol

NCT #: NCT02332915

Title: Effect of Intensity of Treatment on Rehabilitation of Acquired Apraxia of Speech

Date: October 3, 2020

Protocol:**Participants**Inclusion Criteria:

- At least 4 months post onset of focal brain injury
- Chronic acquired apraxia of speech and aphasia
- Native English speaker
- Age: 21 – 90 years
- Pure tone hearing adequate to pass screening at 35 dB at 500, 1000, and 2000 Hz least one ear, or if aided, or verification from an audiological examination that hearing was adequate for conversational level speech.
- Negative histories for alcohol and/or substance abuse and neurological conditions other than stroke; self-reports verified by medical record review
- Performance within normal limits on the *Test of Nonverbal Intelligence-4* (Brown, Sherbenou, & Johnsen, 2010).

AOS diagnostic criteria (McNeil, Robin, & Schmidt, 1997; 2009)

- Slow rate of speech
- Sound errors which included a predominance of distortions
- Syllable segregation
- Relatively consistent trial-to-trial articulation errors
- Prosodic abnormalities.

A battery of tasks was administered to elicit speech samples from which to judge presence/absence of AOS characteristics: 1) motor speech programming protocol (Duffy, 2013),

and 2) word and sentence repetition tasks (Wambaugh, Kalinyak-Fliszar et al., 1998; Wambaugh, West, & Doyle, 1998; and Mauszycki & Wambaugh, 2008). AOS symptoms were evident in at least some, but not necessarily all, of the preceding speech elicitation tasks. The diagnosis of AOS was initially made by each participant's primary clinician (one of the study research speech-language pathologists) and then was verified by the principal investigator.

Language assessments:

- *Western Aphasia Battery-Revised (WAB-R; Kertesz, 2007)*
- Nicholas & Brookshire Discourse Elicitation Battery (Nicholas & Brookshire, 1993)

Demographic data collected:

- Age
- Months post-onset
- Etiology
- Area of brain damage
- Years of Education
- Premorbid handedness
- Race/ethnicity
- Hemiparesis
- Marital status

Experimental Design

A combined group and single-case experimental design (SCED) was used. The group design component was a two-phase, cross-over design and the SCED component was a multiple

baseline designs (MBD) across behaviors and participants. This report is focused on the results of the group design.

Accuracy of articulation of two sets of experimental words (see “Experimental Stimuli”) was measured repeatedly prior to treatment (see “Probes” for additional detail). For each participant, treatment (SPT-Traditional [SPT-T] or SPT- Intense [SPT-I]) was then applied to one set of experimental words while probing continued with both experimental sets. A two week, no-treatment interval followed the first treatment phase and a two-week maintenance probe was completed at the end of the interval. Repeated probing of the set of items to be treated in the second treatment phase during the no treatment interval (as part of the SCED) ensured that performance was stable prior to the application of treatment with that set. Then, the alternate treatment was applied to the remaining set of items. Follow-up probes were conducted at 2 and 8 weeks following the second treatment phase.

Treatment Order and Experimental Set Assignment. Quasi-randomized assignment was combined with participant matching to assign participants to one of two treatment orderings (i.e., SPT-I → SPT-T or SPT-T → SPT-I). We aimed to have a balance of aphasia severity and AOS severity reflected in the treatment orders. The first participant enrolled was randomly assigned to a treatment condition. Each subsequently enrolled participant was “matched” to a previously enrolled participant and assigned to the opposite group if he/she had the same aphasia type, had an AQ within 10 points of the match, and had the same AOS severity rating. When a match did not exist, then the participant was randomly assigned to a treatment order. Please note that the purpose of the investigation was not to compare performance relative to treatment order as all participants received both treatments. The matching and random assignment was conducted to minimize possible confounds associated with treatment order.

As indicated previously, each participant received both SPT-T and SPT-I. Two sets of experimental words were devised for each participant (described below). Those sets were randomly assigned to treatment condition to assist in controlling for influence of stimuli on treatment outcome.

Experimental Stimuli and Probe Procedures

Stimuli. As indicated, two sets of words were individually developed for each participant. For each set, there were three subsets, each of which represented a different sound target.

Pretreatment assessment of word production was used to identify specific sounds that were difficult for the participant to produce. There were a total of 39 words per set, with 24 items designated for treatment and 15 items designated for generalization measurement. Across the participants, stimuli included monosyllabic words, multisyllabic words, and words in phrases.

Probes. Production of the experimental words was elicited in probes. During probes the examiner presented each word verbally, one at a time in random order, and asked the participant to repeat the word as accurately as possible. No feedback concerning accuracy of production was provided; only general encouragers (e.g., you're trying hard) were used. The treatment items were included in probes to measure the *acquisition effects* of treatment and the untreated exemplars of trained items were used to measure the *response generalization* effects of treatment (see Dependent Variable). All probe sessions were audio recorded.

Probes were conducted throughout all phases of the study. Prior to all treatment, three separate probes were completed with all stimuli. During each treatment phase, six probes were conducted. During the two-week no-treatment interval, the "to be treated" set was probed an additional three times to establish a second baseline before the second treatment. Follow-up probes were completed at 2 and 8 weeks post each treatment phase.

Dependent Variable

The dependent variable was accuracy of articulation of a target sound or sounds produced in words elicited in the probes. A single score of correct or incorrect was used for each experimental item. Scoring was completed using on-line, modified narrow transcriptions supplemented and verified with audio recordings. The target sound(s) for each experimental word was/were identified and determined to be accurately or inaccurately produced on the basis of the transcription. Then, the word containing the target sound(s) was given a score of “correct/incorrect”. For each subset of items for each participant, the percentage of words in which the target sounds(s) was produced correctly was tallied from the verified, online productions; the subsets were further separated into trained and untrained subsets. These percentages served as the dependent variables for all analyses.

Target sounds were required to be produced without distortion in the correct syllable of the word. Multisyllabic words were required to have the correct number of syllables so that location accuracy could be judged. For words embedded in a phrase, the phrase word had to be attempted in order for the target sound (in the other word member of the phrase) to be scored as accurate. However, accurate production of the non-targeted phrase word was not required.

The *first complete* production was scored. If the entire target item was produced and there was an error on the target sound(s) and then the participant self-corrected the error, that item was scored as incorrect. However, if there was a false-start (the entire target item was not produced initially) followed by a correct production, then the complete production was scored as correct.

Treatment

The treatment under study was Sound Production Treatment (SPT; Wambaugh et al., 1998). SPT utilizes the therapeutic techniques of modeling/repetition, contrastive practice, orthographic cueing, integral stimulation, and articulatory cuing. These techniques are applied using a response-contingent hierarchy as follows:

1. The speech/language pathologist (SLP) produced a verbal model of the word or phrase and requested a repetition. If monosyllabic words were the treatment targets, sub steps were used for the purposes of contrastive practice upon an incorrect production (e.g., Wambaugh & Mauszycki, 2010; Wambaugh & Nessler, 2004). If multisyllabic words were the target, then contrastive practice was not used and the next step was attempted.
2. The SLP used printed letters/word to indicate the sound in error, directed the participant to attend to the target sound, provided another verbal model, and requested a repetition.
3. The SLP used integral stimulation - “watch me, listen to me, say it with me” - and attempted simultaneous production until a correct production was achieved, with a maximum of three attempts. In cases where a phrase is used, the entire phrase was attempted.
4. The SLP provided articulatory cuing appropriate for the sound production error and then repeated the procedures used in the previous step. Only the target word was practiced (not the entire phrase).
5. The SLP presented the next item.

Verbal feedback concerning the correctness of production of the sound target was provided immediately after each response. Since the hierarchy is response-contingent, ensuing steps of the hierarchy are completed *only* after an erroneous production. Following a correct response and provision of feedback, the next item was presented. The steps of the hierarchy are not reversed following a correct response.

The SPT hierarchy was applied to each treatment item repeatedly in a treatment session. The treatment sessions were approximately one hour long excluding probes. One treatment trial consisted of application of the SPT hierarchy to each of the 24 treatment items. As many treatment trials as possible were completed in a given treatment session. The number of treatment trials per session varied within and across participants and corresponded to the number of errors that occurred because more errors required use of more steps of the hierarchy. Although number of treatment trials varied, the length of each treatment session was carefully controlled to be between 50 and 60 minutes in length and was consistent within and across participants.

Number of treatment sessions was equivalent across treatment phases for each participant. Twenty-seven hourly sessions were completed in each treatment phase. For the intense treatment phase, SPT-I, three treatment sessions were conducted per day, for three days per week, for a total of three weeks. For the non-intense treatment phase, one treatment session was conducted per day, for three days per week, for a total of three weeks.

ASHA certified research SLPs conducted all treatment sessions. Accommodations to treatment schedule were made as needed (e.g., illness, vacations, holidays). Each participant selected his/her treatment location which remained constant throughout the study (i.e., participant's residence, research laboratory, or university clinic).

Reliability

Dependent Variable. Twenty percent of all probes (including all SCED probes) were quasi-randomly selected for rescoring by a research SLP who had not provided treatment; random selection occurred for all phases of the study. The audio recordings of probe sessions were used for rescoring. The reliability SLP was blinded to the assignment of lists to treatment phase and to assignment of items as treated or untreated. Point to point agreement was calculated for scoring of each item and percent agreement was calculated for each probe. Agreement for scoring each word/target as correct/incorrect ranged from 81% to 97%, with the average being 90%.

Independent Variable. A research SLP who had not participated in a given participant's treatment scored audio recorded treatment sessions for accuracy of implementation of treatment. Ten percent of all treatment sessions were randomly selected and were scored for administration of specific treatment components: 1) accurate administration of steps of the treatment hierarchy – 99 %; 2) presentation of all treatment words in each trial – 99%; 3) correct utilization of randomization and blocking – 98%, and 4) treatment session length of 50-60 minutes within +/- 5 minutes – 98%.

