Cover: Statistical Analysis Plan

NCT #: NCT02332915

Title: Effect of Intensity of Treatment on Rehabilitation of Acquired Apraxia of Speech

Date: October 3, 2020

Statistical Analyses

Effect Sizes

Sets of effect size values (d-values) were calculated for each participant as an indication of magnitude of change for *treated items* and *untreated items*: 1) pre-treatment/baseline vs. 2-week follow-up – Intense Phase Items and pre-treatment vs. 2-week follow-up – Traditional (non-intense) Phase Items.

For the pre-treatment versus follow-up comparisons, the three baseline probes immediately preceding application of treatment were used along with the probe completed at two weeks post-treatment. The d-values were derived using the following equation: $ES = (M_{A2} - M_{A1}) / SD_{A1}$. In this equation, “A1” indicates the baseline values and “A2” indicates the 2 week follow up value.

The experimental design was a cross-over design in which each participant received each intensity of treatment in separate, sequential phases (i.e., each participant received two phases of treatment). The arms of the design are designated as Intense First and Traditional First. The arms reflect counterbalancing of order of treatment administration. Order of treatment was not an analysis of interest; there is no evidence to suggest that treatment order would be a pertinent factor in treatment response. The comparison of interest was treatment intensity – Intense versus Traditional treatment phases. Consequently, the data from the Intense phase of treatment for all 24 participants was analyzed relative to the data from the Traditional phase of treatment for all 24 participants.

Descriptive statistics are shown in Tables 1 and 2. Relative to SPT benchmark effect sizes described by Bailey, Eatchel, and Wambaugh (2015) large effect sizes were found for baseline to treatment phase comparisons for treated items for the group for both SPT- Traditional and SPT – Intense, with average effect sizes of 28.9 and 19.7, respectively. For untreated items, large effect sizes

were found for both SPT-Traditional (d=8.1) and SPT-Intense (d=7.9) in for the group. As reflected by the minimum and maximum values in Tables 1 and 2, there were wide ranges of effect sizes found across the individuals.

Table 1

*Effect Size (Δ -values) Descriptive Statistics for **Treated Items** by Treatment Condition for the Group of 24 Participants*

Condition	Comparison	Mean	SD	Minimum	Maximum
d-values					

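### The Traditional-minus-Intense contrast carries some avoidable noise from chance differences between word sets, because d still depends on starting accuracy and baseline accuracy by condition is neither adjusted for nor reported

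*Protocol*

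**What the plan says.** Under Stimuli, the protocol states that "two sets of words were individually developed for each participant". Each set had 39 words (24 treated, 15 for generalization) built on three target sounds. Under Treatment Order and Experimental Set Assignment it adds: "Those sets were randomly assigned to treatment condition to assist in controlling for influence of stimuli on treatment outcome". No step is described that equates the two sets on baseline accuracy.

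Under Probes: "Prior to all treatment, three separate probes were completed with all stimuli". The set reserved for the second phase was then probed three more times in the two-week break between phases.

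In the SAP (Effect Sizes), d = (M_A2 − M_A1)/SD_A1. For this, "the three baseline probes immediately preceding application of treatment were used along with the probe completed at two weeks post-treatment". For the comparison, "the data from the Intense phase of treatment for all 24 participants was analyzed relative to the data from the Traditional phase". The test, described after Table 2, is a two-tailed dependent t-test, or Wilcoxon signed rank if normality fails. It has no covariate. Tables 1 and 2 give the mean, SD, minimum and maximum of d by condition, and no baseline accuracy.

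**The concern.** Pairing removes differences between participants. It does not remove differences between the two sets that one participant worked on, because each condition has its own words and sounds. Random assignment balances set difficulty on average over repetitions of the trial, not necessarily in these 24 pairs.

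Subtracting the baseline mean does not free d from the starting level. A set that starts higher has less room to gain and, away from floor, a larger probe-to-probe SD. Both push d down whatever the intensity.

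The trial's main finding is a difference of 9.2 in mean d on treated items. What is at stake is how precisely that difference is estimated, and whether a reader can tell how alike the two conditions' word sets were at the start.

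**Working it through.** **1. Reproducing the reported test (treated items).** Inputs: means 28.9 and 19.7 (Table 1), t(23) = 2.698, n = 24.

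- Difference = 28.9 − 19.7 = 9.2.
- SE = 9.2/2.698 = 3.41. SD of differences = 3.41 × √24 = 16.7.
- Two-sided p on 23 df = .0128, as stated. 95% CI = 9.2 ± 2.069 × 3.41 = 2.15 to 16.25.
- Untreated items: t(23) = .0735 gives p = .942, also as stated.

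**2. Does d depend on starting accuracy after subtraction?** The documents give no baseline or follow-up accuracy, so follow-up is assumed to be 80%. Each probe is treated as binomial on 24 words, with SD = √[p(1 − p)/24]. The last column is simulated, with three baseline probes, one follow-up probe and zero-SD cases left out.

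| Baseline | Expected gain (points) | Binomial SD (points) | Gain/SD | Simulated median d |
|---|---|---|---|---|
| 5% | 75 | 4.4 | 16.9 | 19.0 |
| 10% | 70 | 6.1 | 11.4 | 13.6 |
| 20% | 60 | 8.2 | 7.3 | 8.7 |
| 30% | 50 | 9.4 | 5.3 | 6.4 |
| 40% | 40 | 10.0 | 4.0 | 4.6 |

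From 5% to 40% the gain falls to 40/75 = 53% of its value, but median d falls to 4.6/19.0 = 24%. The rest comes through SD_A1.

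**3. Is the paired test biased?** Null trials were simulated with 24 participants, baselines of 10 to 35%, follow-up averaging 80%, and random set effects with SD 0, 5, 10 or 15 points (all assumed). The mean difference was about 0 and type I error was 4.6% to 5.8%. There is no material bias.

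**4. How much noise could adjustment remove from d?** In the same trials, the difference in d correlated with the difference in baseline at −0.23, −0.33, −0.48 and −0.59. The SD of the estimate, unadjusted then adjusted, was:

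- 2.007 and 2.006 (set SD 0): variance ratio 1.00
- 2.084 and 1.997 (5 points): 0.92
- 2.348 and 2.060 (10 points): 0.77
- 2.668 and 2.218 (15 points): 0.69

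These runs used as covariate the same probes that define d, so the two share measurement error and the gain is flattered. Simulations over a range of baselines gave variance ratios on d of 0.81 to 1.03 with those probes, and 0.85 to 1.05 with the probes taken before any treatment.

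**5. Percentage correct.** With mean baseline 5 to 38% and set SD 0.4 to 0.8 logit, one set of runs gave ratios of 0.97 to 1.04 at 5–12% baseline and 0.53 to 0.82 at 27–38%. Another gave 1.01 to 1.06 at 14% or less and 0.47 to 0.97 at 28–38%.

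**6. Size of a typical chance shift.** Over the settings tried, a one-SD mean imbalance between sets moved the contrast by about 0.2 to 1.8 d. That is 0.2/3.41 = 0.06 to 1.8/3.41 = 0.53 of the SE.

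**7. Could adjustment undo p = .0128?** Let ρ be the size of the correlation between the difference in d and the baseline difference; it is unknown. Holding the estimate at 9.2 and ignoring the small extra term for observed imbalance, SE_adj = 3.41 × √[(1 − ρ²) × 23/22], on 22 df.

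| ρ | SE_adj | p | 95% CI |
|---|---|---|---|
| 0 | 3.49 | .015 | 1.97 to 16.43 |
| 0.3 | 3.33 | .011 | 2.30 to 16.10 |
| 0.5 | 3.02 | .006 | 2.94 to 15.46 |
| 0.7 | 2.49 | .001 | 4.04 to 14.36 |

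The SE falls only when ρ² exceeds 1/23, that is, ρ above about 0.21. The estimate would also move, by an amount with SD ρ × 3.41. The lower limit is the downward move that would bring p to .05. In SDs that is 2.30/1.02 = 2.2, 2.94/1.71 = 1.7 and 4.04/2.39 = 1.7 for ρ = 0.3, 0.5 and 0.7. For untreated items p stays at .92 to .94.

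**The case against.** The strongest reply is that nothing is wrong with the test. Sets were randomized to condition within participant, so leftover set difficulty is random error already inside the SE of 3.41. The baseline is used: d subtracts each set's own mean, and the second set is re-baselined before its treatment. Target sounds were also chosen because that participant found them difficult, which narrows the spread. An unadjusted paired analysis is legitimate, and covariate adjustment is a matter of efficiency. All of this stands. A reader might infer that word-set difficulty biases the comparison, or that baseline is ignored; the documents support neither.

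The simulations are also not calibrated to the trial. If three equal probes are given the smallest non-zero SD (0.577 words), d cannot exceed 24/0.577 = 41.6, yet Table 1 has maxima of 49.1 and 53.1. Mean d near the Table 1 values needed baselines of roughly 4 to 13%. There, a mean imbalance of 5 points or more arose in at most 8% of simulated trials. So the sizes above are ranges under assumptions, not estimates for this trial.

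Finally, the results are known. Replacing the main test now would add an analyst's choice after the fact. That stands too, and it limits the remedy to an added analysis.

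Two points are left unanswered: d depends on starting level after subtraction, and the baseline balance that would settle how much this matters is measured but not shown.

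**Conclusion.** The point holds as one of efficiency and reporting. The paired test is valid. Chance imbalance between word sets adds noise to the contrast, part of which could be removed with data already collected, and readers cannot see how large the imbalance was.

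The expected reduction in variance on d is about 0 to 15%. It would be larger only if the sets differed widely (31% in the most extreme setting, with the covariate that flatters the gain). On percentage correct, little is gained at baselines below about 15%, and the gain can be substantial near 30 to 40%. These figures rest on assumed baseline and follow-up accuracies and binomial probes.

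A reader might go further and infer that set difficulty explains the 9.2 difference. The documents do not support that. A typical chance shift is at most about half an SE, and adjustment alone is unlikely to overturn p = .0128. It cannot be ruled out, because the adjusted estimate needs participant data. The firmest part is the missing baseline accuracy by condition.

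**What to change.** 1. Print mean baseline accuracy (with SD) by condition in Tables 1 and 2, for the probes taken before any treatment and for the probes used in d.
2. Beside the reported paired test, add a regression across the 24 participants: D_i = α + β X_i + error. D_i is the Traditional-minus-Intense difference in outcome. X_i is the Traditional-minus-Intense difference in accuracy on the three probes made before any treatment. Report α with its 95% CI as the adjusted intensity effect.
3. Do not use the second baseline as covariate. For the set treated second, those probes follow the first treatment phase and could carry generalization from it.
4. Run it for d and for percentage correct (the numerator of d, in points), for treated and untreated items. Label it as added after the results were known.
5. State what is done if residuals are clearly non-normal, since the Wilcoxon fallback takes no covariate.

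Cost: one degree of freedom (23 to 22), a few lines of text and no new data. If baselines are near floor, precision on either scale may be unchanged or slightly worse (variance ratios up to about 1.05).

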Intense	BL vs 2 week FU	19.7	12.6	5.2	49.1
Traditional	BL vs 2 week FU	28.9	17.2	6.5	53.1

BL = baseline; Tx = treatment; wk = week

Bailey et al. (2015) benchmarks: small = 5.90, medium, = 7.12, large = 10.19 for baseline to follow-up phase comparisons

Table 2

*Effect Size (Δ -values) Descriptive Statistics for **Treated Items** by Treatment Condition for the Group of 24 Participants*

Condition	Comparison	Mean	SD	Minimum	Maximum
d-values					
Intense	BL vs 2 week FU	7.9	5.6	-4.1	34.6

Traditional	BL vs 2 week FU	8.1	8.9	-1.0	20.9
--------------------	-----------------	-----	-----	------	------

BL = baseline; Tx = treatment; wk = week

Bailey et al. (2015) benchmarks: small = 2.59, medium, = 4.23, large = 6.47 for baseline to follow-up phase comparisons

Comparisons of average group effect sizes were completed using parametric statistics (i.e., dependent *t*-tests, two-tailed) when possible and the nonparametric analogs when normality tests were failed (i.e., Wilcoxon Signed Rank test). For the *treated items*, results of a dependent *t*-test revealed that there was a statistically significant difference between treatment intensity conditions, with $t(23) = 2.698$, p (two-tailed) = .0128. For the untreated items, results of a dependent *t*-test revealed that there was not a statistically significant difference between treatment intensity conditions, with $t(23) = .0735$, p (two-tailed) = .942. The sample mean of treatment TRAD These tests indicate that for the *treated items*, the 2 week follow-up effect size sample mean for Traditional intensity treatment exceeded that for the Intense treatment. Conversely, for the *untreated items*, the 2 week follow-up effect size sample means did not differ by an amount great enough to exclude the possibility that any difference was due to random sampling variability.

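### The d-values in SAP Table 1 do not follow from the protocol's dependent variable and the SAP's formula unless an unstated rule was applied

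*Protocol*

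**What the plan says.** The protocol's section on experimental stimuli and probes gives the structure: "For each set, there were three subsets, each of which represented a different sound target". It gives the sizes as "There were a total of 39 words per set, with 24 items designated for treatment and 15 items designated for generalization measurement". The Dependent Variable section adds "A single score of correct or incorrect was used for each experimental item" and describes the tally: "For each subset of items for each participant, the percentage of words in which the target sounds(s) was produced correctly was tallied". It continues that "the subsets were further separated into trained and untrained subsets", and then: "These percentages served as the dependent variables for all analyses".

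The SAP (Effect Sizes) computes d for each participant as follow-up minus baseline mean, divided by the baseline SD, from three baseline probes and one probe at two weeks. It reports large effects for treated items, Traditional then Intense, "with average effect sizes of 28.9 and 19.7, respectively". The benchmark under Table 1 is "small = 5.90, medium, = 7.12, large = 10.19 for baseline to follow-up phase comparisons". The paired tests have 23 degrees of freedom, so each participant contributes one d per condition.

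Neither document says how three subset percentages become one d, which divisor the SD uses, what happens when the three baseline probes are identical, or on how many words the benchmark was defined.

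**The concern.** With words scored right or wrong, the smallest non-zero SD of three baseline probes is fixed by the number of words in the unit. So d has a ceiling, and the ceiling rises with the number of words. A d on 8 words and a d on 24 words are on different scales. If the reported values lie above the ceiling for the stated unit, something in the stated definition is wrong or missing.

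At stake is the only significant group result, the treated-item difference in favour of Traditional. A colleague who followed the two documents could not arrive at Table 1, and so could not confirm the paired test or the benchmark class.

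**Working it through.** **Inputs.** Three subsets per set; 24 treated and 15 untreated words; items scored 0 or 1 (protocol). Three baseline probes, one follow-up probe, d = (A2 − mean A1)/SD A1; Table 1 Intense mean 19.7, SD 12.6, range 5.2 to 49.1, and Traditional mean 28.9, SD 17.2, range 6.5 to 53.1 (SAP). Assumption: equal subsets, so 24/3 = 8 and 15/3 = 5 words.

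**Reproducing the SAP's tests.** On 23 df, t = 2.698 gives p = .0128 and t = .0735 gives p = .942, as printed. For treated items the mean difference is 28.9 − 19.7 = 9.2, so the SD of the differences is 9.2 × √24/2.698 = 16.7 and the implied correlation about 0.40. The test agrees with the Table 1 means and SDs. The question is how the d-values themselves arose.

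**Ceiling for d on k words.** The largest finite d comes from baseline counts 0, 0, 1 (mean 1/3) and a perfect follow-up. The SD is 1/√3 = 0.577 words with divisor n−1, or √2/3 = 0.471 with divisor n. Hence d max = (k − 1/3)/SD. Enumerating all three-probe baselines confirms this.

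| Words in unit | Divisor n−1 | Divisor n |
|---|---|---|
| 8 (treated subset) | 13.28 | 16.26 |
| 5 (untreated subset) | 8.08 | 9.90 |
| 24 (all treated) | 40.99 | 50.20 |
| 15 (all untreated) | 25.40 | 31.11 |

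**Subset unit, treated items.** Both means (19.7 and 28.9) exceed 13.28 and 16.26. Averaging three subset d-values does not help for any split of the 24 words, because (24 − 3 × 1/3) × √3/3 = 13.28. Other ways of combining equal subsets also fall short of the maxima of 49.1 and 53.1:

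- nine baseline values in one SD: 23.67 (25.10 with divisor n);
- an SD pooled within subsets: 23.67 (28.99);
- the sum of three subset d-values: 39.8 (48.8).

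**Words needed.** k must be at least d × SD + 1/3. A mean of 28.9 needs 28.9 × 0.577 + 0.333 = 17.02, so 18 whole words (14 with divisor n), even with every participant at the ceiling. The value 49.1 needs 29 (24) words, and 53.1 needs 31 (26).

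**All 24 words.** Averaging three equal subset percentages at each probe gives the same percentage as pooling. The means fit. The value 53.1 exceeds both ceilings (40.99 and 50.20), and 49.1 fits only with divisor n.

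**Two unstated routes that could reach the printed values.**

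- *Unequal subsets averaged without weights.* As an illustration, suppose a 6/8/10 split. If the only baseline successes are 1, 2 and 2 words in the 10-word subset, the averaged percentages are 3.33, 6.67 and 6.67 (mean 5.56, SD 1.92 with divisor n−1). Perfect follow-up gives 94.44/1.92 = 49.1. Averages of 6.67, 6.67 and 9.72 give 52.3, and other baselines go higher still.
- *A replaced zero SD.* With a 100-point gain, 53.1 implies a baseline SD of 100/53.1 = 1.9 points. The smallest non-zero SD (divisor n−1) is 7.2 points on 8 words and 2.4 on 24. A substituted SD could be smaller.

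**Table 2.** The untreated means (7.9 and 8.1) lie about at the 5-word ceiling of 8.08. The maxima (34.6 and 20.9) exceed it, and 34.6 also exceeds both 15-word ceilings. However, the Intense row cannot be right as printed. With mean 7.9, minimum −4.1, maximum 34.6 and n = 24, the sum of squares is at least 26.7² + 12.0² + 14.7²/22 = 866.7, so the SD is at least √(866.7/23) = 6.1, and 5.6 is printed. The table is also titled as treated items, although the text uses it for untreated ones.

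**The case against.** The protocol says that subset percentages were the dependent variables; it does not say that a d was computed within each subset. The SAP places d at participant level. The natural bridge is to average the three percentages at each probe and then form one d. On that reading the subset ceiling does not apply, the Table 1 means are attainable, and with unequal subsets so are values as large as the maxima. All 24 participants also appear in the tables, so a zero-SD rule may well have existed. This stands as far as it goes: the printed values are not impossible under every reading. But each reading that reaches the maxima adds a step that neither document states.

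A reader might go further and infer that the analysed unit was not the stated one, presumably all 24 or 15 words pooled. The documents do not support that, because the pooled sets also fail to give 53.1 and 34.6. A reader might also infer that *large* rests on a mismatched scale. That is not shown either: the benchmark's unit is not given, so the match is unverified, not disproved.

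Finally, both conditions use the same item counts, and no change in the Intense versus Traditional contrast has been demonstrated. That is correct. A change of unit alters each participant's baseline SD and is not a common rescaling, so the result could move, but its direction and size are unknown without the probe scores.

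**Conclusion.** The point holds as a conflict between the stated dependent variable, the stated formula and the printed figures. At subset level the ceiling is 13.3 (16.3 with divisor n) against treated means of 19.7 and 28.9. With all 24 words it is 41.0 (50.2) against a maximum of 53.1. The reported d-values and the test t(23) = 2.698 do not follow from what is written, unless subsets were unequal and averaged without weights, or an unstated rule replaced zero baseline SDs.

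The conclusion rests on Table 1. Table 2 is weaker evidence because its Intense row is internally impossible and 34.6 may be a misprint. The sizes 8 and 5 are inferred; equality does not matter if three finite subset d-values are averaged, but it matters if percentages are averaged first. The cause cannot be settled from the documents: the unit, the SD definition, a zero-SD rule and a table error all remain possible. Nor can it be determined whether the benchmark applies.

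**What to change.** Correct the Dependent Variable section and the SAP so that both give the same four things: one participant-level unit for treated and for untreated items, the way the three subsets are combined (with their sizes), the SD divisor, and the handling of a zero baseline SD, with the number of participants and conditions affected.

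Recompute Tables 1 and 2 and both paired tests from the existing probe scores under that definition. Correct any entry that cannot be reproduced, including the Table 2 Intense row and the Table 2 title. Keep the label *large* only if the benchmark is confirmed to use the same unit and SD rule; otherwise report d without it.

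The cost is a few sentences in each document and a small re-analysis with no new data. The d-values, the p-value or the label may become less favourable.
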